Exploratory outcomes for which we anticipate greater than 80% power include epinephrine and sympathetic nervous system tone. Discrepant data exist for the effects of leptin on thyroid function (specifically, T3) based on the model used (lipodystrophy versus 10% weight loss), and this study should help to clarify whether this effect does or does not exist in lipodystrophy. We do not anticipate observing significant changes in resting energy expenditure; however, because this procedure is minimal risk, we feel that it will be important to document negative results for this outcome. Certain outcome measures, such as liver triglyceride (for which liver size was a proxy in the table, above), and insulin sensitivity, appear to progressively change over time with leptin replacement. For these outcomes, a 2 week intervention may be insufficient to observe statistically significant results. For other outcome measures, such as intramyocellular triglyceride, preliminary data on the short-term effects of leptin are not available, but effects, if present, are unlikely to be detectable by two weeks.

Therefore, in addition to obtaining data after 2 weeks of leptin withdrawal or initiation, we will restudy subjects in the leptin-naïve group 6 months (range is 5-9 months) after leptin initiation to look for changes that may not be detectable by 2 weeks.

Because some subjects may not complete the study, or may not have interpretable data for each outcome, we plan to enroll up to 20 subjects in each group in order to have 10 completers per group.

Statistical Methods for Data Analysis

Data will be analyzed separately for the leptin naïve and leptin treated subjects. This is done because the effects of leptin withdrawal after long-term treatment are likely to be different from the effects of leptin initiation after long-term deficiency.

Analysis of Primary Outcomes

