Measurements in each of the primary outcomes will be analyzed using the paired t-test (for normally distributed variables) or Wilcoxon paired test (for skewed variables) to test if there is any significant difference between the two study periods (on and off leptin) for each group (leptin naïve and leptin treated), respectively. In addition, mixed models incorporating baseline (pre-diet) parameters as covariates will be used to adjust for any effects of the inpatient, metabolic diet, independent of leptin's effects. For variables with more than 2 measurements during Period 2, repeated measure linear models (Mixed model or GLM) will be used to study the time effect, using pooled data from the 2 periods. Potential covariates to be explored in the model include: Age, sex, race, percent body fat, lean mass, body weight, type of lipodystrophy, and endogenous leptin level. To account for any deviation from the isocaloric protocol diet, actual caloric intake will be included as a covariate in mixed model analyses.

Additional correlations between variables within and between each of the major outcome categories (glucose metabolism, lipid metabolism, and energy expenditure) will be analyzed using either Pearson's correlation or simple linear regressions. These include the following:

1. Association between change in total body insulin sensitivity and changes in hepatic insulin sensitivity, fasting plasma glucose, and C-peptide
2. Association between change in rate of lipolysis, and changes in fasting triglycerides and fatty acid turnover
3. Association between insulin sensitivity and ectopic lipid stores, and rates of lipolysis and fatty acid turnover
4. Association between change in total energy expenditure and changes in resting energy expenditure, skeletal muscle work efficiency, spontaneous physical activity, thyroid function, catecholamines, and cardiac autonomic nervous system tone.

Analysis of Secondary and Exploratory Outcomes

Methods for analysis of secondary outcomes will be similar to those for primary outcomes. In addition, we will perform analysis to study the following associations between categories of outcome measures:

1. Association between the Ectopic Lipid measurements with Glucose and Lipid measurements
2. Association between the Endocrine measurements with Energy Expenditure measurements

Analysis of long-term data

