Additional follow up data will be obtained and analyzed 6 to 12 months after leptin initiation for the leptin naïve patients. Long-term follow-up measurements for this group will be compared with the baseline using paired comparisons. Time-dependent effects will also be investigated using repeated measures analysis. The analysis methods to be used are similar to those used in the primary outcome analyses.

By Group Comparisons

Although most of the analyses will be performed separately for leptin naïve vs. leptin treated patients due to the consideration stated previously, exploratory analyses will be carried out to compare the two study groups. These analyses include:

1. Comparison of outcomes and baseline characteristics by group will be performed using t-test or rank test, depending on the distribution of measurement compared
2. Model analysis using general linear models will be performed by including group as a factor

Study Implementation

Subjects will be admitted to the Metabolic Research Unit in the NIH Clinical Center. They will remain as inpatients throughout the 19 day duration of the short-term portion of the study. After admission, they will undergo a history and physical examination, and baseline labs will be obtained. Baseline phenotyping will include measurement of resting energy expenditure, hemoglobin A1c, and fasting lipid panel, glucose, insulin, and C-peptide. Fasting triglycerides and hemoglobin A1c will be used to assess subject eligibility in the leptin treated group. Additional labs used to assess subject eligibility in all subjects include electrolytes, BUN, creatinine, CBC, and a pregnancy test for female patients of reproductive potential. Height, weight, blood pressure, resting pulse, temperature, and anthropometric data (e.g. skin fold measurements, waist circumference, etc.) will be obtained. Additionally, the clinical testing that was formerly included in 02-DK-0022 will be done: ECHO, OGTT, liver/abdominal and pelvic ultrasounds.

Diet

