After baseline phenotyping, subjects will be placed on a low fat (20±5% protein, 25% fat, 55±5% carbohydrate), weight maintenance diet from the metabolic research kitchen. Total caloric requirements will be estimated by the research dietitian. Due to the low proportion of body fat in people with lipodystrophy, all male and female subjects' energy needs will be estimated using the Mifflin St. Joer equation for males with an activity factor of 1.3. Upon admission, resting energy expenditure will be measured and dietary energy will be adjusted as needed. The diet may be adjusted during the first few days, but will be continued for the remainder of the study without change.

In the leptin naïve group, appetite is expected to decrease following leptin initiation during Period 2, although the early time course of this effect is not known. Subjects will be encouraged to eat all food presented to them by the metabolic kitchen in order to maintain the isocaloric nature of the diet throughout both periods. However, if they are unable to consume all food, the uneaten portion will be returned to the metabolic kitchen and weighed to document the extent of deviation from the isocaloric diet. Analogously, in the leptin-treated group, subjects may feel hungry after leptin withdrawal, but will only be permitted to eat the food provided by the metabolic kitchen.

In prior studies of leptin replacement in lipodystrophy, subjects had a mean weight loss of only 2.8 kg (4.6% of initial body weight) after 4 months of leptin replacement. Hence, changes in body weight during the course of the 3 week inpatient portion of this study are not expected to be clinically significant. Because each subject will be compared with him/herself in the leptin deficient versus leptin replaced state, maintaining constant (isocaloric) food intake during both conditions will allow assessment of the energy-intake independent effects of leptin.

Medications

Leptin Treatment

Any subject starting leptin on this study will get it through NIH under IND, regardless of whether or not they fit in an FDA approved category. After the follow-up visits, subjects who are eligible will be transitioned to commercial drug supply through their physician. Subjects undergoing leptin withdrawal may receive leptin under IND or FDA approved commercial drug, depending on the timing of their study participation.

Details of leptin administration and dosing for the subjects who are leptin treated are as follows:

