9. Metabolic chamber: The room calorimeter is a specially constructed room designed to assess the metabolism of human subjects. Designed as a walk-in “pull” calorimeter, it is an open circuit unit that draws conditioned room air into the room calorimeter at the same flow rate as it is extracted into the gas analysis system⁴². Each of the three rooms is equipped with toilet and sink with privacy screen, treadmill, bed, desk, and computer with access to television and other forms of entertainment. In addition to the detailed measurements using portable activity monitors, a general physical activity level is also measured continuously through a wall mounted monitoring device (microwave sensor). Food and fresh water is passed through an air-lock drawer system. In this rapid-response room calorimeter, the sleeping energy expenditure, diet induced thermogenesis⁴³ and the specific energy costs of prescribed non-intense physical activity types⁴⁴ will be assessed. A recent study of our first room calorimeter showed better than ± 85 kcal/day (95% Confidence Interval) reproducibility in total energy expenditure in 10 healthy normal subjects (total energy expenditure ranged from 1551 to 3559 kcal/day), and ± 0.023 in average and sleeping RQ. Compared to the literature, this is the most precise system to date. Continuous nursing supervision with telemetry cardiac monitoring is a standard procedure to enhance patient safety⁴⁶⁻⁴⁸. Subjects will wear standardized clothing while in the metabolic chamber in order to increase uniformity in measurements of skin temperature and thermal comfort. Subjects will have a 30 minute treadmill walking period in the chamber in order to bring out any effects of altered skeletal muscle work efficiency on total energy expenditure. Subjects will stay in the metabolic chamber at the end of Period 1, in the middle and end of Period 2, and during the follow-up visit for subjects in the leptin-naïve group.

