10. Glucose and Lipid Turnover: Stable isotope tracers will be used to measure glucose and lipid turnover. Endogenous glucose production will be measured using steady-state infusion of [6,6-²H₂] glucose tracer. The fractional rate of gluconeogenesis will be measured using steady-state oral dosing of deuterated water (²H₂O)⁴⁹. The rate of lipolysis will be measured using steady-state infusion of deuterium-labeled ²H₅-glycerol, and the fatty acid turnover rate will be measured using steady-state infusion of [U-¹³C₁₆] palmitate. Subjects will fast after 8 pm. A total of 3 grams per kg lean body mass of ²H₂O will be given in four divided doses every two hours at 9 pm, 11 pm, 1 am, and 3 am in order to enrich the subject’s body water pool to approximately 0.5% ²H₂O. Beginning at ~5 am, a primed [6,6-²H₂]glucose infusion will be given for 3 hours, after which blood samples to measure isotope enrichment will be measured over a period of 30 minutes at steady state. Two hours after the [6,6-²H₂]glucose infusion begins, a primed ²H₅-glycerol infusion, and unprimed [U-¹³C₁₆] palmitate infusion will be given for one hour, and

isotope enrichment will be measured over a period of 30 minutes at steady state. Tracer studies will be performed at the end of Period 1, in the middle and end of Period 2, and during the follow-up visit for subjects in the leptin-naïve group. To assess the effects of hyperinsulinemia on glucose turnover, the glucose tracer infusion will be continued during the euglycemic, hyperinsulinemic clamp study, below, with blood samples for tracer enrichment obtained during the steady-state period of the clamp.

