11. Euglycemic Hyperinsulinemic Clamp: This is the gold-standard test to measure insulin sensitivity. For insulin treated subjects, an overnight insulin drip may be given beginning at 6 pm the night prior to the clamp to maintain euglycemia. After an 8-hour fast, insulin will be infused at a dose of 120 mcU/m²*minute. This dose is designed to suppress endogenous glucose production and near-maximally stimulate glucose uptake in this group of very insulin resistant subjects. For a small number of subjects with extreme insulin resistance (requiring more than 200 units of insulin per day), higher doses of insulin may be used during the clamp study to create a state of hyperinsulinemia above the subject's baseline state. 20% dextrose enriched with 2.5% [6,6-²H₂] glucose tracer will be infused at a variable rate to maintain blood glucose at approximately 90 mg/dL. If subjects remain hyperglycemic without dextrose infusion after 1 hour of insulin infusion (by which time maximum insulin effect is expected), the clamp will be considered "failed" and will be prematurely terminated. During the insulin infusion, blood samples (0.5 mL) will be obtained every 5 minutes to measure blood glucose at the bedside. At steady state, the rate of dextrose infusion provides an estimate of insulin-stimulated glucose disposal. Additional samples will be drawn to measure the glucose and lipid tracers (described above), insulin, and other hormone levels. Due to the blood volumes and inconvenience of this test to participants, it will be performed once at the end of Period 1, once at the end of Period 2, and during the follow-up visit for subjects in the leptin-naïve group. If technical problems occur with a clamp study (e.g. IV failure or failure to attain steady-state glucose and insulin levels), the clamp may be repeated if blood volume limits permit.

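### Pre-diet covariates cannot remove the effect of the inpatient diet; the within-group tests stay confounded with time and need a supporting comparison of the two groups' changes

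*Combined protocol and SAP*

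**What the plan says.** The primary comparison is end of Period 1 against end of Period 2, by paired t-test or Wilcoxon test within each group. Under Statistical Methods for Data Analysis: "Data will be analyzed separately for the leptin naïve and leptin treated subjects". Under Analysis of Primary Outcomes the plan adds that "mixed models incorporating baseline (pre-diet) parameters as covariates will be used to adjust for any effects of the inpatient, metabolic diet". Actual caloric intake is a further covariate, and repeated-measures models are planned to study the effect of time.

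On timing, the Diet section says "After baseline phenotyping, subjects will be placed on a low fat" (weight-maintenance) diet, and then: "The diet may be adjusted during the first few days, but will be continued for the remainder of the study without change". Under Study Implementation, baseline phenotyping consists of resting energy expenditure, HbA1c, fasting lipids, glucose, insulin and C-peptide, and an oral glucose tolerance test is also done. The three primary outcomes are measured later:

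- Clamp (insulin sensitivity): "it will be performed once at the end of Period 1, once at the end of Period 2, and during the follow-up visit".
- Tracer study (lipolysis): "Tracer studies will be performed at the end of Period 1, in the middle and end of Period 2".
- Chamber (total energy expenditure): "Subjects will stay in the metabolic chamber at the end of Period 1, in the middle and end of Period 2".

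Under By Group Comparisons, "exploratory analyses will be carried out to compare the two study groups". These cover outcomes and baseline characteristics by group, and general linear models with group as a factor. A comparison of the groups' changes, or a group-by-period term, is not named.

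**The concern.** The trial asks what leptin does when intake is fixed. Leptin-naïve subjects all go from off to on and leptin-treated subjects all go from on to off. No group keeps the same leptin status through both periods. Anything else that changes between the end of Period 1 and the end of Period 2 therefore enters the within-group difference: continued adaptation to the diet, the hospital stay, or the daily treadmill walking.

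The plan recognises that the diet may have effects of its own and says a model will take them out. If that model cannot do so, a reader will credit the estimates with an adjustment they do not have. A shared drift could produce a significant result in one group and hide a real one in the other.

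**Working it through.** **1. Is there a pre-diet value to adjust with?** Not for the primary outcomes. The sections quoted above place the first clamp, tracer study and chamber stay at the end of Period 1, on the diet. The schedule table under Study Procedures agrees. Only resting energy expenditure, the fasting laboratory values and the glucose tolerance test precede the diet.

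**2. Would such a covariate help if it existed?** Write subject i's outcome in period p as y(i,p) = u(i) + βb(i) + τ·[p = 2] + error, where b(i) is the pre-diet value and τ = leptin effect + drift. The term βb(i) is the same in both periods and cancels from y(i,2) − y(i,1). In a fitted mixed model on simulated data the period coefficient was 0.917 with the covariate and 0.917 without it. In 4,000 simulated trials with no leptin effect, a drift of 0.5 SD and n = 10, regressing change on centred baseline gave the same mean estimate as the plain paired analysis (0.50). Rejection was 0.283 with the covariate and 0.287 without.

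The other planned terms do not fill the gap. The intake covariate deals with departures from the diet, not with the shared effect of being on it. The repeated-measures time effect uses the same single-order data, so time and leptin stay aliased within each group.

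**3. The plan's own power figures.** Inputs are the means and SDs in the table under Sample Size Justification, with n = 10. For Power 1 the SD of the difference is √(s₁² + s₂²), and d = difference / SD.

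- Total energy expenditure: √(15.8² + 4.7²) = 16.48; d = 16/16.48 = 0.971.
- Insulin sensitivity, 1-month source: √(0.79² + 1.1²) = 1.354; d = 1.2/1.354 = 0.886.
- Lipolysis: √(36² + 7²) = 36.67; d = 53/36.67 = 1.445.

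The stated Power 1 values (0.92, 0.87, 0.99) are matched within a point by a one-sided normal approximation, Φ(d√10 − 1.645) = 0.923, 0.876, 0.998. Power 2 is matched within about a point with SD = s₁ + s₂. A two-sided paired t-test (df 9) gives 0.780, 0.704 and 0.981 for Power 1. The two-sided values are used below because the plan tests for any difference.

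**4. Effect of drift on the paired test.** Noncentral t, df 9, noncentrality k√10, where k is the drift in SDs of the paired difference. The documents give no k, so this is an assumed range.

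| Drift k | 0 | 0.25 | 0.5 | 1.0 |
|---|---|---|---|---|
| Two-sided error, no leptin effect | 0.050 | 0.109 | 0.293 | 0.803 |

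A drift of 0.5 SD is 8.2 percentage points of energy expenditure, 0.68 mg/kg/min of insulin sensitivity, or 18.3 units of lipolysis. If it opposes a true withdrawal effect, d becomes d − 0.5. Power then falls from 0.780 to 0.266, from 0.704 to 0.194, and from 0.981 to 0.758 respectively.

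**5. The comparison of changes.** Two-sample t on the changes, 10 per group, df 18, standard error √(2/10) = √0.2 SD. In the same simulation (equal drift) it rejected in 4.6% of trials. If drift differs between the groups by 0.25, 0.5 or 1.0 SD, its error is 0.083, 0.185 or 0.562. Its two-sided power, with Power 1 SDs / Power 2 SDs, is:

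| Assumed effects | Energy expenditure | Insulin sensitivity (1 month) | Lipolysis |
|---|---|---|---|
| Equal and opposite (2d) | 0.98 / 0.91 | 0.96 / 0.77 | >0.99 / >0.99 |
| One half the other (1.5d) | 0.87 / 0.70 | 0.80 / 0.52 | >0.99 / 0.97 |
| One group only (d) | 0.54 / 0.38 | 0.47 / 0.27 | 0.86 / 0.74 |

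**The case against.** The best reply has four parts.

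- **Scope and safeguards.** The claim concerns an additional mixed model, and the plan does not say the paired tests are diet-adjusted. The design also limits drift: a 5-day run-in, the same diet at both measurements, standardised exercise and an intake covariate. This stands in part. These features reduce a shared drift but do not remove it. The diet may still be adjusted in the first few of the five days, and Period 2 runs 14 days more. Results in opposite directions in the two groups would also argue against a single common drift, but only informally.
- **Already planned.** If the outcome is taken to be change, group as a factor is the proposed contrast. The text is open to that reading but does not say it, and a group main effect on the measurements is a different quantity. The request therefore sharpens an existing plan.
- **Equal drift is doubtful.** This stands. Several exclusions apply to treated subjects only, insulin is handled differently in the two groups, and the Introduction puts leptin's effect on spontaneous intake at about half, so the fixed diet may be a larger change for naïve subjects. Naïve subjects may also leave food, while treated subjects may not eat more. If only the naïve group drifted, by 0.5 SD, the contrast would have 19% error while the treated group's paired test stayed at 5%. The contrast can support the paired tests but not replace them.
- **The drift sizes are assumed, and the largest is extreme.** This also stands. A drift of 1.0 SD is 16.5 points of energy expenditure, more than the 16-point leptin effect in the table. The only related yardstick in the documents is chamber reproducibility of ±85 kcal/day, or 2.4% to 5.5% of the range given (85/3559 to 85/1551). It comes from healthy subjects and does not measure inpatient drift.

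**Conclusion.** The concern holds and should be fixed. That the stated adjustment cannot do what is claimed follows from the schedule and from algebra, and needs no assumption about drift. The size of the harm does depend on one. At 0.25 to 0.5 SD the paired test's error is 11% to 29% instead of 5%, and 0.5 SD in the wrong direction would leave power of about 0.27 for energy expenditure and 0.19 for 1-month insulin sensitivity. The run-in may keep the true drift at the low end or below.

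The design itself survives. The plan explains why a randomised crossover is not feasible, and nothing here asks for one. What is missing is a statement that the within-group results are confounded with time, and a named analysis that uses the second group to address the part of the drift both groups share.

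**What to change.** 1. Under Analysis of Primary Outcomes, delete the statement that pre-diet covariates adjust for the diet. They may stay as prognostic covariates.
2. Keep the separate within-group tests and label their results as before-after changes not adjusted for period effects.
3. For each of the three primary outcomes, pre-specify a supporting comparison of the groups' changes (end of Period 2 minus end of Period 1) in subjects with both values, by two-sample t-test, or rank-sum test if skewed. Alternatively, fit a mixed model with group, period and group-by-period terms, keeping the group main effect, and test the interaction.
4. State the limits: the contrast assumes a similar period effect in two non-randomised groups; half the difference averages the initiation and withdrawal effects, which the plan expects to differ; and a non-significant contrast does not rule out an effect in one group.

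The cost is a wording correction and three supporting analyses of data already collected. The equal-drift assumption cannot be tested with these data. Appendix D reports 28 patients already enrolled, so the addition should be dated and marked as made after enrolment began.
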